7.2.1. Inclusion criteria

1. Patients under the age of 15 years at the initiation of treatment with this product
2. Patients with invasive fungal infections

The indications, and dosage and administration of this product are as follows. The latest package insert should be referred to when administering this product.

[INDICATIONS]

Severe mycosis as follows:

- Invasive aspergillosis, Pulmonary aspergilloma, Chronic necrotic pulmonary aspergillosis.
- Candidemia, Esophageal candidiasis*, Candidal peritonitis, Bronchopulmonary candidiasis.
- Cryptococcal meningitis, Pulmonary cryptococcosis.
- Fusariosis.
- Scedosporiosis. * Only for tablets and dry syrup

[DOSAGE AND ADMINISTRATION]

<for Intravenous Use>

Adult	Voriconazole is administered by intravenous drip infusion at the dose of 6 mg/kg twice daily on day 1 and 3 mg/kg or 4 mg/kg twice daily from day 2 onward.
Children (Aged 2 to <12 and ≥12 whose body weight is less than 50 kg)	9 mg/kg as voriconazole twice daily on day 1 and 8 mg/kg twice daily from day 2 should be given intravenously. Dose may be increased if poorly responded by 1 mg/kg at a time, and dose in intolerant patients should be reduced by 1 mg/kg at a time.
Children (Aged ≥12 whose body weight is 50 kg or more)	6 mg/kg as voriconazole twice daily on day 1 and 4 mg/kg twice daily from day 2 should be given intravenously.

<Tablet>

Adult (body weight ≥40 kg)	A recommended oral dose of voriconazole is 300 mg/dose twice daily between meals on day 1, and 150 or 200 mg/dose twice daily between meals on day 2 and thereafter. Dose may be increased depending on condition of patients or if poorly responded; provided that a total daily dosage should not exceed 400 mg/dose twice daily on day 1 and 300 mg/dose twice daily on day 2 and thereafter.
----------------------------	--

Adult (body weight <40 kg)	A recommended oral dose of voriconazole is 150 mg/dose twice daily between meals on day 1, and 100 mg/dose twice daily between meals on day 2 and thereafter. Dose may be increased from day 2 onward depending on condition of patients or if poorly responded; provided that a total daily dosage should not exceed 150 mg/dose twice daily.

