Children (Aged 2 to <12 and ≥12 whose body weight is less than 50 kg)	After the administration of Voriconazole injection, a recommended maintenance oral dose of voriconazole following injection therapy is 9 mg/kg/dose twice daily between meals. Dose may be increased by 1 mg/kg at a time if poorly responded, and dose in intolerant patients should be reduced by 1 mg/kg at a time (unless the dosage was at its maximum 350 mg, in which case, dose should be reduced by 50 mg at a time). A total daily dosage should not exceed 350 mg/dose twice daily.
Children (Aged ≥12 whose body weight is 50 kg or more)	After the administration of Voriconazole injection, a recommended maintenance oral dose of voriconazole following injection therapy is 200 mg/dose twice daily between meals; which may be increased up to 300 mg/dose twice daily if poorly responded.

<Dry Syrup>

Adult (body weight ≥40 kg)	A recommended oral dose of voriconazole is 300 mg/dose twice daily between meals on day 1, and 150 or 200 mg/dose twice daily between meals on day 2 and thereafter. Dose may be increased depending on condition of patients or if poorly responded; provided that a total daily dosage should not exceed 400 mg/dose twice daily on day 1 and 300 mg/dose twice daily on day 2 and thereafter.
Adult (body weight <40 kg)	A recommended oral dose of voriconazole is 150 mg/dose twice daily between meals on day 1, and 100 mg/dose twice daily between meals on day 2 and thereafter. Dose may be increased from day 2 onward depending on condition of patients or if poorly responded; provided that a total daily dosage should not exceed 150 mg/dose twice daily.
Children (Aged 2 to <12 and ≥12 whose body weight is less than 50 kg)	After the administration of Voriconazole injection, a recommended maintenance oral dose of voriconazole following injection therapy is 9 mg/kg/dose twice daily between meals. Dose may be increased by 1 mg/kg at a time if poorly responded, and dose in intolerant patients should be reduced by 1 mg/kg at a time (unless the dosage was at its maximum 350 mg, in which case, dose should be reduced by 50 mg at a time). A total daily dosage should not exceed 350 mg/dose twice daily.

Children (Aged ≥ 12 whose body weight is 50 kg or more)	After the administration of Voriconazole injection, a recommended maintenance oral dose of voriconazole following injection therapy is 200 mg/dose twice daily between meals; which may be increased up to 300 mg/dose twice daily if poorly responded.

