5.4. Subgroups

Subgroup analyses of safety will be performed for the following patient background factors. Levels in parentheses are levels of subgroups, and underlined levels are the reference for calculation of risk ratio and risk difference.

- Hepatic dysfunction [absent, present]
- Renal dysfunction [absent, present]
- Age (children 1) [newborns (<1 month after birth), infants (≥ 1 month to <1 year), younger children (≥ 1 to <7 years), children (≥ 7 to <15 years)]
- Age (children 2) [<2 years, ≥ 2 years]
- Diagnostic name (name of infection) [invasive aspergillosis, pulmonary aspergilloma, chronic necrotic pulmonary aspergillosis, candidemia, esophageal candidiasis, candida peritonitis, bronchopulmonary candidiasis, cryptococcal meningitis, pulmonary cryptococcosis, fusariosis, scedosporiosis, other invasive fungal infections, others]
- Severity [mild, moderate, severe]
- Fever unresponsive to antibacterial agents [absent, present]
- Use of concomitant medications requiring precautions for coadministration [absent, present]
- Concomitant antifungal agents [absent, present]
- Prior medications (antifungal agents) [absent, present]
- Treatment period [<1 week, ≥ 1 to <2 weeks, ≥ 2 to <4 weeks, ≥ 4 to <8 weeks, ≥ 8 to <12 weeks, ≥ 12 to ≤ 16 weeks]
- Long-term treatment [≤ 12 weeks, >12 weeks]
- Dose on the first day (mg/kg) [<6, ≥ 6 to <7, ≥ 7 to <8, ≥ 8 to <9, ≥ 9 to <10, ≥ 10 , unknown]
- Mean maintenance dose (mg/kg) [<6, ≥ 6 to <7, ≥ 7 to <8, ≥ 8 to <9, ≥ 9 to <10, ≥ 10 , unknown]

Subgroup analyses of safety will be performed for the following:

- Pregnant and parturient women (pregnancy confirmed)
- Presence or absence of overdose^a

Patients who may meet contraindications in the package insert of Vfend (hereinafter referred to as contraindicated patients) will be extracted based on separately specified criteria, and subgroup analyses of safety will be performed.

Subgroup analyses of efficacy (clinical response) will be performed for the following patient background factors. Levels in parentheses are levels of subgroups, and underlined levels are the reference for calculation of risk ratio and risk difference.

- Hepatic dysfunction [absent, present]
- Renal dysfunction [absent, present]
- Age (children 1) [newborns (<1 month after birth), infants (≥ 1 month to <1 year), younger children (≥ 1 to <7 years), children (≥ 7 to <15 years)]
- Age (children 2) [<2 years, ≥ 2 years]

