In the safety analysis set, clinical response analysis set, and mycological response analysis set, the number and proportion of the following patients will be tabulated.

- Concomitant medications
- Contraindicated concomitant medications
- Concomitant medications requiring precautions for coadministration
- Prior treatment (antifungal agents) for infection for which Vfend is administered
- Reasons for discontinuation of prior treatment for infection for which Vfend is administered

- **Status of treatment of Vfend**

In the safety analysis set, the following status of treatment of Vfend will be tabulated: Furthermore, dose will be tabulated separately for patients aged <12 years and ≥12 years

whose body weight is less than 50 kg and those aged ≥ 12 years whose body weight is 50 kg or more.

- Treatment period [<1 week, ≥ 1 to <2 weeks, ≥ 2 to <4 weeks, ≥ 4 to <8 weeks, ≥ 8 to <12 weeks, ≥ 12 to ≤ 16 weeks, >16 weeks]
- Treatment period (long-term treatment) [≤ 12 weeks, >12 weeks]
- Treatment period (days) (continuous)
- Dose on the first day (mg) (continuous)
- Dose on the first day (mg) [<50 , ≥ 50 to <100 , ≥ 100 to <150 , ≥ 150 to <200 , ≥ 200 to <250 , ≥ 250 to <300 , ≥ 300 to <350 , ≥ 350 , unknown]
- Dose on the first day (mg/kg) (continuous)
- Dose on the first day (mg/kg) [<6 , ≥ 6 to <7 , ≥ 7 to <8 , ≥ 8 to <9 , ≥ 9 to <10 , ≥ 10 , unknown]
- Mean maintenance dose (mg) (continuous)
- Mean maintenance dose (mg) [<50 , ≥ 50 to <100 , ≥ 100 to <150 , ≥ 150 to <200 , ≥ 200 to <250 , ≥ 250 to <300 , ≥ 300 to <350 , ≥ 350 , unknown]
- Mean maintenance dose (mg/kg) (continuous)
- Mean maintenance dose (mg/kg) [<6 , ≥ 6 to <7 , ≥ 7 to <8 , ≥ 8 to <9 , ≥ 9 to <10 , ≥ 10 , unknown]
- Mean maintenance dose of injection alone (mg) (continuous)
- Mean maintenance dose of injection alone (mg) [<50 , ≥ 50 to <100 , ≥ 100 to <150 , ≥ 150 to <200 , ≥ 200 to <250 , ≥ 250 to <300 , ≥ 300 to <350 , ≥ 350 , unknown]
- Mean maintenance dose of injection alone (mg/kg) (continuous)
- Mean maintenance dose of injection alone (mg/kg) [<6 , ≥ 6 to <7 , ≥ 7 to <8 , ≥ 8 to <9 , ≥ 9 to <10 , ≥ 10 , unknown]
- Mean maintenance dose of oral preparations (tablet + dry syrup) alone (mg) (continuous)
- Mean maintenance dose of oral preparations (tablet + dry syrup) alone (mg) [<50 , ≥ 50 to <100 , ≥ 100 to <150 , ≥ 150 to <200 , ≥ 200 to <250 , ≥ 250 to <300 , ≥ 300 to <350 , ≥ 350 , unknown]

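### The mg/kg dose subgroups pool two paediatric dosing bands, and mean maintenance dose can fall as a result of an adverse drug reaction, so their risk ratios are not clean dose comparisons

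*SAP*

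**What the plan says.** SAP 5.4 names "Dose on the first day (mg/kg" and "Mean maintenance dose (mg/kg" as subgroup factors for both safety and clinical response. Each has cut-points at 6, 7, 8, 9 and 10 mg/kg and is not split by dosing band or route. SAP 8.2.3.4 treats them as background factors and applies the risk ratio and risk difference of 8.1.3 to any ADR, then to serious ADRs. SAP 8.2.4.4 repeats the subgroup analysis for clinical response. SAP 6.4 names no covariates. SAP 8.2.3.5 sends factors with a risk ratio of at least 2 or at most 0.5 to further tabulation.

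The protocol (7.2.1) doses two paediatric bands differently.
- For ages 2 to under 12, or 12 and over below 50 kg: "9 mg/kg as voriconazole twice daily on day 1 and 8 mg/kg twice daily from day 2 should be given intravenously". By mouth, "a recommended maintenance oral dose of voriconazole following injection therapy is 9 mg/kg/dose twice daily between meals", with a 350 mg limit per dose.
- For age 12 and over at 50 kg or more: "6 mg/kg as voriconazole twice daily on day 1 and 4 mg/kg twice daily from day 2 should be given intravenously". By mouth, "a recommended maintenance oral dose of voriconazole following injection therapy is 200 mg/dose twice daily between meals", rising to at most 300 mg.

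In the first band, "dose in intolerant patients should be reduced by 1 mg/kg at a time".

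SAP 8.2.2 does recognise the bands: "dose will be tabulated separately for patients aged <12 years" (together with those 12 or over below 50 kg) and for the remaining older, heavier patients. It also gives injection-alone and oral-alone means. Both splits stand only in the descriptive exposure tables.

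**The concern.** Factors affecting safety and effectiveness are a stated objective, and dose is an obvious candidate. Two features blur the dose comparison.

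1. **Pooling.** If nominal mg/kg is set by age and weight, a contrast between a low and a high bin is partly a contrast between older, heavier children and the rest. This touches both dose variables.
2. **Reverse causation.** Mean maintenance dose is known only after treatment. If an ADR leads to a reduction, the patient's average falls and the ADR is counted in a lower bin. The reduction step of 1 mg/kg equals the bin width, and the nominal doses of 8 and 9 mg/kg sit on lower bin edges, so even a late reduction moves the patient down. This touches mean maintenance dose only.

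For clinical response the direction is the opposite: the protocol allows an increase when response is poor, so poor responders can drift into higher bins.

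The SAP already respects timing elsewhere. In 8.2.3.1, medicines started after the last onset of the event are left out of the concomitant-medication tables. Dose has no such rule.

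**Working it through.** The documents give no figure for the dose subgroups, so there is none to reproduce. The nearest planning figures are 100 patients and rates of 19.0% (hepatic toxicity) and 42.9% (visual events). All ADR risks and reduction shares below are assumptions. Doses are read as mg/kg per administration, which is how the protocol states them.

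**Step 1: where the nominal doses fall (protocol 7.2.1 against the SAP 5.4 bins)**

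| Band | IV day 1 | IV from day 2 | Oral maintenance |
|---|---|---|---|
| 2 to <12 y, or ≥12 y and <50 kg | 9 | 8 | 9, until the 350 mg limit binds at 350/9 = 38.9 kg; 350/50 = 7.0 near 50 kg |
| ≥12 y and ≥50 kg | 6 | 4 | at most 200/50 = 4.0, or 300/50 = 6.0 after an increase |

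The bands do not overlap at their nominal doses. The quoted dosing table starts at age 2, so it places no nominal dose on younger children, who are nevertheless eligible and analysed.

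**Step 2: effect of pooling.** Suppose dose has no effect within a band. The crude risk ratio of the 8 to <9 bin against the <6 bin is then the ratio of the band risks:
- 30% against 30% gives 1.0
- 30% against 45% gives 0.67
- 30% against 60% gives 0.50
- 40% against 20% gives 2.0

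Pooling misleads only if the bands differ in risk, but it can then reach the 8.2.3.5 screen in either direction.

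**Step 3: effect of reductions on mean maintenance dose.** Take the first band only, half on 8 and half on 9 mg/kg. ADR risks are 30% and 45%, a true risk ratio of 1.5. A share f of ADR patients is reduced, and each drops one bin.

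- Risk at mean ≥9: 0.45(1 − f) / (1 − 0.45f)
- Risk at mean <9: (0.30 + 0.45f) / (1 + 0.45f)
- Risk in the 8 to <9 bin alone: (0.30 + 0.15f) / (1 + 0.15f)

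| f | Risk, ≥9 | Risk, <9 | RR, ≥9 vs <9 | Risk, 8 to <9 | RR, ≥9 vs 8 to <9 |
|---|---|---|---|---|---|
| 10% | 0.405/0.955 = 0.424 | 0.345/1.045 = 0.330 | 1.28 | 0.315/1.015 = 0.310 | 1.37 |
| 25% | 0.3375/0.8875 = 0.380 | 0.4125/1.1125 = 0.371 | 1.03 | 0.3375/1.0375 = 0.325 | 1.17 |
| 50% | 0.225/0.775 = 0.290 | 0.525/1.225 = 0.429 | 0.68 | 0.375/1.075 = 0.349 | 0.83 |

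Setting the first two risks equal gives 0.15 = 0.5625f, so the ≥9 versus <9 ratio reverses above f = 27%. For adjacent bins, 0.15 = 0.3975f, so reversal needs f above 38%.

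**Step 4: no true dose effect.** With 35% at both doses, the ≥9 versus <9 ratio is [0.35(1 − f)/(1 − 0.35f)] / [(0.35 + 0.35f)/(1 + 0.35f)]:
- f = 10%: 0.326/0.372 = 0.88
- f = 25%: 0.288/0.402 = 0.72
- f = 50%: 0.212/0.447 = 0.47, which crosses the 0.5 screen

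**Step 5: grouping by dose before onset.** Patients then stay in their starting groups. The ratio is 0.45/0.30 = 1.5 in Step 3 and 0.35/0.35 = 1.0 in Step 4.

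**The case against.** The strongest reply has four parts.

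- **Mean maintenance dose is not defined**, so averaging over the whole course is a reading and not stated text. That stands. It is the natural reading, and the missing definition needs filling in any case.
- **First-day dose is fixed before any reduction**, so the SAP already holds a dose comparison free of reverse causation. That stands. Route mixing is also minor there, because the protocol's oral dosing in children follows injection.
- **The study is exploratory.** SAP section 4 has no decision rule, protocol 7.9 admits that confounding may be poorly controlled, and the screen leads only to another table. The dose question named for hepatic and visual events (continuing against discontinuing patients) is a separate description. This limits the consequence but does not make the risk ratios readable.
- **The second band may be small**, being only patients aged 12 to 14 at 50 kg or more, and its share is not given. Contrasts among the higher bins then lie mostly within one band. That stands.

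A reader might go further and infer that the bins mostly stand for age, weight and route, or that the plan will make lower doses look over twice as toxic. For example, take 85 patients at 8 mg/kg, 42 with an ADR and 13 of them reduced. That gives 13/13 against 29/72, a ratio of 2.48. The documents do not support this. The inputs are invented, and nobody else may be in the 7 to <8 bin. Yet the 350 mg oral limit puts children from 350/8 = 43.75 kg to just under 50 kg in or at the edge of that bin. If 15 of the 85 are such patients, 7 with an ADR, the ratio is (20/28)/(22/57) = 1.85. With 4 reductions instead of 13 it is (11/19)/(31/66) = 1.23.

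**Conclusion.** The point holds in a limited form. Both mg/kg subgroup analyses pool bands that the protocol doses differently, so contrasts with the lowest bins partly reflect age and weight. For mean maintenance dose alone, reductions after an ADR attenuate a true dose association and, if frequent, reverse it. Under the assumed risks, a true 1.5 appears as 1.28, 1.03 or 0.68 at 10%, 25% or 50% reduced for ≥9 versus <9, and as 1.37, 1.17 or 0.83 for adjacent bins. Which contrast the SAP would report cannot be told here, because the underlining that marks its reference levels is lost in the available text.

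The result rests on a course-average reading, on assumed risks, and on a reduction share that the documents do not give. Reversal is a possibility and not a prediction, and it does not extend to first-day dose. The harm is misreading dose as a factor and misdirecting the 8.2.3.5 screen. No error rate is at stake. This is a cheap improvement. Nothing here judges which dose is right.

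**What to change.** In SAP 5.4:

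1. Present both mg/kg dose subgroup analyses by the age and weight band already used in 8.2.2. If the band aged 12 or over at 50 kg or more is small, list its patients instead.
2. For the safety comparison, define mean maintenance dose as the mean from day 2 to the day before first ADR onset. Without an ADR, run it to the last dose within the tabulation period. List separately the patients whose first ADR comes before any maintenance dose.
3. Name first-day dose as the comparison free of reverse causation. Show the injection-alone and oral-alone means as supportive tables only. A required route split would spread about 100 patients over six bins and two routes and would often meet the 8.1.3 rule that withholds ratios at 5 patients or fewer. An ADR during injection also leaves no oral dose before onset.
4. State that mean maintenance dose against clinical response cannot be read as a dose effect, because dose may be increased for poor response.

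The cost is SAP wording and one derived variable, from the dosing records and onset dates already collected (protocol 7.3.2 and 7.3.8). The downsides are somewhat fewer patients per bin, different exposure windows for patients with and without an ADR, and residual confounding by weight where the 350 mg oral limit binds.

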6. RESEARCH QUESTION AND OBJECTIVES

This study is intended to assess the following items, etc. for the safety and effectiveness of Vfend 200 mg for Intravenous Use, Vfend Tablets 50 mg, Vfend Tablets 200 mg, and Vfend Dry Syrup 2800 mg (hereinafter referred to as this product) in daily clinical practice for invasive fungal infections in children and review the necessity for further special investigation and post-marketing clinical study.

- Unknown adverse reactions
- Occurrence of adverse reactions under actual clinical settings
- Factors considered to affect the safety and effectiveness of this product

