7.3.2. Targeted drug use record

The following will be recorded for the treatment status of this product.

- (1) Dosage form
- (2) Dose
- (3) Body weight used for calculation of adjustment of this product
- (4) Frequency of dose
- (5) Treatment period

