- Diagnostic name (name of infection) [invasive aspergillosis, pulmonary aspergilloma, chronic necrotic pulmonary aspergillosis, candidemia, esophageal candidiasis, candida peritonitis, bronchopulmonary candidiasis, cryptococcal meningitis, pulmonary cryptococcosis, fusariosis, scedosporiosis, other invasive fungal infections, others]
- Severity [mild, moderate, severe]
- Fever unresponsive to antibacterial agents [absent, present]
- Use of concomitant medications requiring precautions for coadministration [absent, present]
- Concomitant antifungal agents [absent, present]
- Prior medications (antifungal agents) [absent, present]
- Treatment period [<1 week, ≥ 1 to <2 weeks, ≥ 2 to <4 weeks, ≥ 4 to <8 weeks, ≥ 8 to <12 weeks, ≥ 12 to ≤ 16 weeks]
- Long-term treatment [≤ 12 weeks, >12 weeks]
- Dose on the first day (mg/kg) [<6, ≥ 6 to <7, ≥ 7 to <8, ≥ 8 to <9, ≥ 9 to <10, ≥ 10 , unknown]
- Mean maintenance dose (mg/kg) [<6, ≥ 6 to <7, ≥ 7 to <8, ≥ 8 to <9, ≥ 9 to <10, ≥ 10 , unknown]

^a : Because the upper limit of the dose of oral preparations (tablet and dry syrup) is 350 mg according to the dosage and administration of Vfend in children (aged ≥ 2 to <12 years and ≥ 12 years and weighing <50 kg), patients receiving oral preparations at a dose of >350 mg are defined as overdosed. Although there is no upper limit for injection, patients receiving injection at a dose of >350 mg and ≥ 10 mg/kg are defined as overdosed.

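### SAP 5.4 applies one 350 mg oral overdose limit to every patient, so oral doses above 300 and up to 350 mg in children aged ≥12 years weighing ≥50 kg exceed the printed limit but count as no overdose

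*SAP*

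**What the plan says.** SAP 5.4 lists presence or absence of overdose among the safety subgroups and defines it in footnote a. The footnote first cites the 350 mg oral ceiling for children aged 2 to <12 years, or ≥12 years and under 50 kg. It then states the rule for everyone: "patients receiving oral preparations at a dose of >350 mg are defined as overdosed". For the other route it notes "Although there is no upper limit for injection" and adopts a joint condition of more than 350 mg and at least 10 mg/kg.

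The dosage tables in Protocol 7.2.1 give two paediatric oral bands, with the same limits for tablets and dry syrup. The lighter band has a ceiling of 350 mg per dose twice daily. Children aged ≥12 years and ≥50 kg have a maintenance dose of 200 mg, "which may be increased up to 300 mg/dose twice daily if poorly responded". Enrolment is open to any patient under 15 years, so this heavier band is eligible.

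SAP 8.2.3.4 tabulates patients with at least one adverse drug reaction, and separately those with serious ones, for each factor in 5.4.

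**The concern.** The footnote justifies its threshold by the approved paediatric dosage, so its own standard is whether the dose exceeds the label. For the heavier band it uses the wrong label figure. A child of 13 years and 55 kg given 350 mg orally is above the printed limit. That child, with any adverse reaction, is counted in the overdose-absent row. The purpose of the subgroup is to separate patients dosed above the label from the rest, and for this band it does not do so between 300 and 350 mg.

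**Working it through.** **Inputs.** SAP 5.4 footnote a: oral threshold >350 mg, unconditional. Protocol 7.2.1: oral limit 350 mg per dose (lighter band) and 300 mg per dose (≥12 years and ≥50 kg). Protocol section 6: products are "Vfend Tablets 50 mg, Vfend Tablets 200 mg, and Vfend Dry Syrup 2800 mg", besides the intravenous form. The footnote's dose is read as a single dose, since the ceiling it cites is stated per dose in the protocol.

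**Step 1: reproduce the plan's figure.** 350 mg matches Protocol 7.2.1 for the band that the footnote names. It does not match the heavier band, where the figure is 300 mg.

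**Step 2: apply both rules to the heavier band.** SAP rule: dose > 350. Printed limit: dose > 300.

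| Single oral dose, ≥12 years and ≥50 kg | Above printed limit | SAP flag |
|---|---|---|
| 300 mg | no | absent |
| 301 mg | yes | absent |
| 325 mg | yes | absent |
| 350 mg | yes | absent |
| 351 mg | yes | present |
| 400 mg | yes | present |

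The misclassified window is >300 to 350 mg, at most 350/300 = 1.17 times the limit. Whole-tablet doses are 50a + 200b, hence multiples of 50 mg, and the only one in the window is 350 mg. Dry syrup may allow others.

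**Step 3: try the narrow reading.** If the footnote is meant only for the band it names, the heavier band has no oral overdose rule at all. The same doses stay unflagged.

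**Step 4: look for the gap elsewhere in the SAP.**

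- The mg/kg dose levels in 5.4 do not show it. 350 mg is 350/50 = 7.0 mg/kg at 50 kg, 350/60 = 5.8 at 60 kg and 350/70 = 5.0 at 70 kg. All are below the lighter band's ordinary oral dose of 9 mg/kg.
- The mg classes in SAP 8.2.2 are split by the two bands and show it in part. A constant 350 mg oral maintenance dose falls in the class of 350 mg and above, apart from the permitted 300 mg. A syrup dose between 300 and 350 mg shares a class with 300 mg. A mean can also hide the excess: equal numbers of 200 mg and 350 mg doses average (200 + 350)/2 = 275 mg. These classes are not crossed with adverse reactions.

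**The case against.** The strongest reply is that this hardly matters. In practice the window is close to a single tablet dose, 350 mg. That dose is within the ceiling for a 14-year-old of 49 kg, and it is at most 7 mg/kg in the affected band. Investigators must report overdoses within 24 hours under Protocol 9.1 and 9.4.3. The administration listing in SAP section 9 shows the dosing record, and the 8.2.2 classes display a constant 350 mg dose. The study plans 100 patients and has no decision rule. All of this stands as a limit on the size of the point. None of it changes the tabulated flag, which still puts these patients in the wrong row.

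A reader might go further and infer that the injection rule is also defective. Requiring both more than 350 mg and at least 10 mg/kg makes the trigger max(350/weight, 10) mg/kg: 350/10 = 35 at 10 kg, 350/20 = 17.5 at 20 kg, and a flat 10 from 35 kg upward. The documents do not support calling this an error. The SAP states openly that no injection limit exists, so the rule is a declared convention. Protocol 7.2.1 allows escalation in the lighter band without a printed injection cap ("Dose may be increased if poorly responded by 1 mg/kg at a time"), so a flag at 10 mg/kg alone would mix permitted escalation with overdose. SAP 5.4 also has levels of ≥10 mg/kg for first-day and mean maintenance dose, and 8.2.3.4 tabulates reactions by them. They largely cover the concern below 35 kg, although a brief high dose in mid-course could be averaged away.

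**Conclusion.** The point holds for the oral rule. Under either reading of the footnote, oral doses above 300 and up to 350 mg in children aged ≥12 years and ≥50 kg exceed the printed limit and are not flagged. Doses above 350 mg are flagged under the unconditional reading, and the lighter band is classified correctly.

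The effect is confined to one descriptive safety subgroup. How many patients it touches cannot be computed, because the documents give no weight or dose distribution. A reader might infer that risk ratios for overdose are distorted. That is only one possible reading: 5.4 lists overdose apart from the background factors that carry reference levels, 8.2.3.4 ties the 8.1.3 comparison to background factors, and 8.1.3 suppresses ratios for subgroups of 5 or fewer.

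The conclusion assumes that the footnote's dose is a single dose and that the limits printed in Protocol 7.2.1 still apply. The protocol refers prescribers to the latest package insert.

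**What to change.** Rewrite the oral part of footnote a: overdose is >300 mg per dose for patients aged ≥12 years and weighing ≥50 kg, and >350 mg per dose for all other patients. The words *all other* matter. Protocol 7.2.1 sets no lower age limit and SAP 5.4 has a subgroup under 2 years, so a rule worded only for the two labelled bands would drop children whom the present rule covers. Leave the injection rule as it is.

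Re-derive the flag and report how many patients change class.

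The cost is one footnote and one derived variable. Age is collected under Protocol 7.3.1. Dosage form, dose and "Body weight used for calculation of adjustment of this product" are collected under 7.3.2. SAP 8.2.2 already makes the same split ("dose will be tabulated separately for patients aged <12 years", together with those aged ≥12 years under 50 kg, against the heavier band), with no lower age bound.
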